9.11.2. EDWARDS INTUITY ELITE VALVE EARLY POST-OPERATIVE EXPLANT

Explant of EDWARDS INTUITY Elite Valve is the removal of the registry valve after the index EDWARDS INTUITY Elite Valve System procedure is completed and the patient is physically transported from the operating room with an implanted valve in place. The valve is explanted by accessing the aortic valve site and exposing the valve. Once exposure has been achieved, the surgeon should use a scalpel to cut the three sutures in the inter-commissural region on the sewing cuff of the valve. Once the three sutures have been removed, the surgeon should perform a circumferential blunt dissection around the registry valve. Once a blunt dissection is complete, use forceps to grasp the valve at the commissure and lift the study valve upward from the annulus.

9.11.3. EDWARDS INTUTY ELITE VALVE – LATE POST-OPERATIVE EXPLANT (>30 DAYS)

During the late post-operative period, explantation of the study valve may require that the device and surrounding anatomy be assessed using echocardiography, x-ray, or visually to determine the most appropriate course of action.

9.12. Reoperation/reintervention on the valve without Valve Explant

Reoperation on the registry valve can also occur without a need of the valve removal.

Any percutaneous interventional procedure that repairs, otherwise alters or adjusts a previously implanted prosthesis (registry valve) after the valve was implanted and the patient left the operating room are considered reoperation. In non-surgical category all enzymatic, balloon dilation, interventional manipulation, prosthetic valve PVL fixation, repositioning, or retrieval, and other catheter-based interventions for valve related complications are also considered re-interventions.

9.13. Operative intervention not on the registry valve

If a registry subject experiences complications or otherwise requires additional unplanned operations or interventions, these data should be captured on the Adverse Event CRF forms where applicable in the intervention taken section.

The Adverse Event code should reflect the cause of the intervention

10. Data collection and documentation

10.1. Data collection methods

All required data for this investigation are to be collected with standardized Case Report Forms (CRFs) for individual subjects. Electronic CRFs will be utilized for this investigation. CRFs must be electronically signed by the Principal Investigator or co-Investigator listed in the Delegation of Authority Log. If for any reason the CRFs are unavailable and/or inaccessible, paper CRFs will be provided by the Investigation Sponsor to be completed, signed by the Principal Investigator or designee and submitted to the Investigation Sponsor.

Primary data collection should be drawn from hospital patient chart and operation worksheet (source document). CRFs must be kept current to reflect subject status during the course of the investigation.

Data should be captured in the Case Report Form (CRF) within 2 weeks of the patient visit.

CRF instructions will be provided to assist the Investigator(s) and appropriate investigation staff in the completion of the required CRFs.

10.2. Source documentation requirements

Regulations require that Investigational centers maintain information about any clinical investigation subject's medical records that reflect the data collected in the CRFs. In order to comply with these regulatory requirements, the following information will be maintained as required by the Sponsor monitors and/or regulatory inspectors:

- 1. Medical history and physical condition of the clinical investigation subject before involvement in the clinical investigation sufficient to verify protocol entry criteria**
- 2. Dated and signed notes in the subject's medical record on the day of entry into the clinical investigation.**
- 3. Dated and signed notes, laboratory records, and test reports, from each clinical investigation subject visit with reference to the CRFs for further information, if appropriate (for specific results of procedures and exams).**
- 4. Notations on abnormal lab results and adverse events reported and their resolution.**
- 5. Notes regarding concomitant anticoagulant/antithrombotic medications taken during the clinical investigation**
- 6. Subject's condition upon completion of or withdrawal from the clinical investigation.**
- 7. Source documents related to reported safety endpoints or potential safety endpoints, and device related events, including documentation from outside admissions (admissions not at the enrolling site)**

10.3. Quality control and quality assurance procedures

Data Management personnel will employ a full-featured, relational database application on a central server. The application provides the capability of data collection remotely through the Internet so the participating site personnel may log on the system securely and enter the data. Other data management programming and/or data analyses will be done in the database system through the sponsor's internal network or that of the sponsor's designee.

All subjects' data collected in the system will be extensively verified through data validation programs, database integrity rules, and investigation-specific data entry conventions for data accuracy and logical meaningfulness. Periodic analysis of all subjects' collected data will be performed in order to examine the expected

distributions of data and to identify outliers for possible data entry errors. An audit trail will identify all corrections and changes to the electronic data.

Queries or discrepancies will be entered to clarify discrepancies in the data entered on the CRF. Direct queries to the study coordinator via e-mail or phone are also allowed, but should be documented.

10.4. Protocol Deviations

The protocol deviations are defined as deviations in the informed consent improperly obtained (not signed & dated, not consented); inclusion/exclusion criteria (eligibility and intra-operative criteria); Safety as UADE / USADE not reported within 24 hours of the investigator first learning of the event without documentation.

11. Adverse Events

11.1. General Reporting Requirements

The EDWARDS INTIITY Elite is CE marked; therefore all adverse events should be recorded in accordance with Medical Device Directive 93/42/EEC, MEDDEV 2.12-1 Guidelines on a Medical Devices Vigilance System, ISO 14155:2011(E), and any other regulations as applicable, and as summarized in Table 2.

Adverse event reporting is an investigator's responsibility and decision. Adverse Events (AE) will be identified and captured on the AE CRF throughout the duration of the registry as they occur and will be followed until they are adequately resolved or explained.

In MISSION Registry, all Serious Adverse Events and Device/Procedure Related Events should be reported as soon as possible but no later than within 72 hours (3 calendar days) after the Investigational center first learns of the event.

All Device-Related Deaths and all Unanticipated Adverse Events (not listed in the risk section of the protocol or IFU) or Serious Device-Related Adverse Events should be reported within 24 hours after the investigational center first learns of the event.

Relevant source documents will be provided to Sponsor for evaluation and endpoints adjudication within 15 working days after the Investigational center first learns of the event. That includes source documents records from outside admissions (hospitalizations out of the enrolling site), which are related to reported adverse events/complications.

Notification to the Sponsor should be done via electronic data system by entering an adverse event into the database or if that's impossible an initial notification can be done by fax or email to the assigned Safety personnel

[contact]

In addition, investigational centers are responsible for reporting serious adverse events to their local Regulatory Bodies in accordance with the applicable requirements.

11.2. ADVERSE EVENTS COLLECTED FOR THIS REGISTRY – REGISTRY ENDPOINTS:

All Registry Endpoints and Potential Endpoints will be adjudicated (reviewed) by an independent CEC committee

TABLE 2. SAFETY ENDPOINTS DEFINITIONS

Complication	Definition
All-cause mortality	All cause mortality includes all exspirations of registry subjects as reported from investigational sites/or adjudicated per CEC
Registry valve-related mortality	
Any death caused by structural valve deterioration, nonstructural dysfunction, valve thrombosis, thromboembolism, bleeding event, or operated prosthetic valve endocarditis; death related to reintervention on the operated valve; or sudden, unexplained death (when the cause of death has not been determined by clinical investigation or autopsy findings and the relationship to the operated valve is undefined)
 
Deaths caused by heart failure in patients with advanced myocardial disease and satisfactorily functioning cardiac valves are not counted.

Hemolysis	Plasma-free hemoglobin > 40 mg/dl on two consecutive measurements within 48 hours; or clinical diagnosis of hemolysis evidenced by laboratory testing such as serum hemoglobin, hematocrit, and/or plasma-free hemoglobin (not immunologically based) and/or hemolysis diagnosed elevated serum lactate dehydrogenase (≥ 440 U/L) and/or reduced serum haptoglobin (≤ 37 mg/dL) in the absence of paravalvular leak
Prosthetic Valve Endocarditis	Operated Valve Endocarditis is any infection involving a valve on which an operation has been performed. The diagnosis of operated valve endocarditis is based on one of the following criteria:

CONFIDENTIAL AND PROPRIETARY DATA: This document and the information contained herein may not be reproduced, used, or disclosed without written permission from Edwards Lifesciences SA

	
autopsy findings of abscess, pus, or vegetation involving a repaired or replaced valve; orin the absence of reoperation or autopsy, fulfilling the Duke Criteria for endocarditis (Am J Med 1994; 96:200-9) 
Positive blood cultures are not required for the diagnosis of operated valve endocarditis. Culture-negative endocarditis should refer only to negative blood cultures results and not just the absence of any proof of infection. Morbidities associated with active infection, such as valve thrombosis, thrombotic embolus, bleeding event, or paravalvular leak are included under this category, but not counted in other categories of morbidity.

Thromboembolism (Stroke, TIA and Non-Cerebral Thromboembolic Event)	
Embolism is any embolic event that occurs in the absence of infection (endocarditis) starting from anesthesia time. Embolism may be manifested by a neurologic event or a non-cerebral embolic event.
 
A neurologic event includes any central, new neurologic deficit, whether temporary or permanent and whether focal or global, that occurs after anesthesia was administered.
 
Stroke is a prolonged (>72 hours) or permanent neurologic deficit that is usually associated with abnormal results of brain magnetic resonance imaging or computed tomography. Patients with minimal, atypical, or protean symptoms that lead to radiographic imaging demonstrating an acute ischemic event are considered to have sustained a stroke.
 
Transient Ischemic Attack (TIA) is characterized by fully reversible symptoms of short duration. If radiographic imaging demonstrates an acute central neurologic lesion ("cerebral infarction with transient symptoms"), however, such patients are reclassified as having sustained a stroke. [‡]
 
Multiple or repeated transient events occurring during a short period (a burst or cluster) should be recorded as one event, but documented as a "cluster".
 
The diagnosis of a TIA is defined as complete resolution of new neurological symptoms usually within 1-2 h but always within 24 h and also requires a normal neuroimaging registry and the absence of any other primary medical cause (hypoglycemia, hypoxia, etc.)
 
NON-CEREBRAL EMBOLIC EVENT
 
Non-cerebral embolic event is an embolus documented operatively, at autopsy, or clinically that produces signs or symptoms attributable to complete or partial obstruction of a peripheral artery, excluding deep venous thrombosis (DVT).
 
Emboi consisting of confirmed/documentated nonthrombotic material (e.g., atherosclerosis, myxoma) are not counted. If unable to determine the material then it will be considered embolic.

	
Intraoperative myocardial infarctions are not counted. Postoperative myocardial infarction is also not counted unless the infarction is caused by a coronary thromboembolism (as detected by operation, autopsy, or clinical imaging).

Major Paravalvular Leak	
Major Paravalvular Leak is any paravalvular leak, exclusive of that associated with thrombosis or infection, that leads to intervention or re-operation (with or without symptoms), or that is graded 3+ or greater (with or without symptoms and with or without intervention/ re-operation), or that results in death, or that is 3+ or greater when diagnosed by autopsy.

Major Bleeding	
Major bleeding is bleeding that causes death, hospitalization, or permanent injury (e.g. vision loss) or requires transfusion of 3 or more units of PRBCs.
 
Major bleeding unexpectedly associated with minor trauma should be reported as a bleeding event, but bleeding associated with major trauma or a major operation should not.
 
Minor Trauma examples are subdural hematoma, IC bleed associated with fall, hematuria from catheter
 
Major Trauma/Major Operation examples are a fracture, CT surgery. These will be noted but do not count as events for the analysis.
 
All bleedings requiring hospital admission such as an admission for GI Bleeding, Access Site Hematoma or other source of bleeding should be reported as Major Bleeding.

Reoperation (on the registry valve)	
Re-intervention is any surgical or percutaneous interventional procedure that repairs, otherwise alters or adjusts, or replaces a previously implanted prosthesis or repaired valve (registry valve). In addition to surgical reoperations, enzymatic, balloon dilation, interventional manipulation, repositioning, or retrieval, and other catheter-based interventions for valve related complications are also considered re-interventions. Indications for re-interventions must be reported. Open surgical and percutaneous catheter re-interventions should be listed separately.
 
An explant is defined as a re-intervention resulting in removal of the implanted valve after the patient leaves the operating room with an implanted valve, after the index procedure.

Renal Failure	
An acute event or worsening of renal function resulting in one or more of the following: 1) Increase of serum creatinine to >2.0 mg/dL, and 2x most recent preoperative creatinine level. 2) A new requirement for dialysis postoperatively

Respiratory Failure with need for mechanical ventilation (Post index procedure)	
Respiratory event requiring endotracheal reintubation and ventilator support post index procedure.

New or worsening implant related conduction disturbance requiring a permanent pacemaker implantation	Any new or worsened implant-related cardiac conduction disturbance requiring implantation of permanent pacemaker.
Valve thrombosis	Any thrombus attached to or near an implanted valve that occludes part of the blood flow path, interferes with valve function, or is sufficiently large to warrant treatment. Valve thrombus found at autopsy in a patient whose cause of death was not valve related or found at operation for an unrelated indication should also be reported as valve thrombosis.
Deep sternal wound infection	Deep sternal wound infection involving muscle, bone, and/or mediastinal contents confirmed by positive tissue cultures and requiring intervention (wound opening and excision of tissue ; or re-exploration for washout and treatment) and systemic antibiotics.
Structural Valve Deterioration	Structural valve deterioration includes dysfunction or deterioration involving the operated valve (exclusive of infection or thrombosis), as determined by re-operation, autopsy, or clinical investigation. Clinical investigation should include periodic echocardiographic surveillance. Substantially increased regurgitation or stenosis of the operated valve over time should be reported with quantitative or semi-quantitative methods. The term structural valve deterioration refers to changes intrinsic to the valve, such as wear, fracture, poppet escape, calcification, leaflet tear, stent creep, and suture line disruption of components of a prosthetic valve; it also refers to new chordal rupture, leaflet disruption, or leaflet retraction of a repaired valve.
Non Structural Valve Deterioration	Any abnormality not intrinsic to the valve (do not directly involve valve components) itself that results in stenosis or regurgitation of the operated valve or hemolysis (excludes thrombosis and infection). Examples include: Entrapment by pannus, tissue, or suture, paravalvular leak, inappropriate sizing, inappropriate positioning, Regurgitation as a result of technical error, STJ dilation, dilation of the valve annulus, obstruction of the coronary ostia by the registry valve.

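### The endocarditis row of Table 2 contradicts itself: read literally, valve infection first proven at reoperation in a survivor is left out of the endocarditis rate

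*Combined protocol and SAP*

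**What the plan says.** All the wording at issue is in Section 11.2, Table 2 of the protocol.

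- **Definition.** The endocarditis row begins broadly: "Operated Valve Endocarditis is any infection involving a valve on which an operation has been performed".
- **Diagnostic rule.** The next sentence narrows it: "The diagnosis of operated valve endocarditis is based on one of the following criteria". Two criteria follow.
- **Criterion 1.** "autopsy findings of abscess, pus, or vegetation involving a repaired or replaced valve".
- **Criterion 2.** The Duke criteria, available in "the absence of reoperation or autopsy, fulfilling the Duke Criteria for endocarditis".
- **Related events.** The row adds: "Morbidities associated with active infection, such as valve thrombosis, thrombotic embolus, bleeding event, or paravalvular leak are included under this category", and says they are not to be counted in other morbidity categories.
- **Major paravalvular leak row.** It covers "any paravalvular leak, exclusive of that associated with thrombosis or infection". The non-structural deterioration row likewise excludes infection.
- **Reoperation row.** It covers any re-intervention on the registry valve, has no exclusion for infection, and requires the indication to be reported. Explant is defined in the same row.

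Endocarditis of the study valve is a listed safety endpoint (Sections 7.4 and 12.3). Section 12.3 plans early percentages, linearized late rates and Kaplan-Meier estimates at thirty days and six months. It also plans rates for complications outside the endpoint list.

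**The concern.** Neither criterion uses what the surgeon finds at reoperation. Yet the second criterion is worded as a fallback for subjects who had neither a reoperation nor an autopsy. That condition makes sense only if reoperation findings count in their own right, and no such criterion is listed.

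The subjects affected are those with direct operative proof of infection. If they are left out, the endocarditis rate is too low for a recognised valve complication, and describing safety at 30 days and 6 months is a secondary objective of the registry. The result would also depend on which sentence of the row an adjudicator follows, so the same case could be classified either way.

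**Working it through.** **Step 1: take one subject through the row.** Suppose a subject is reoperated for an infected registry valve, has vegetations seen at surgery, survives, and had not met the Duke criteria beforehand.

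| Sentence in the endocarditis row | Met? | Reason |
|---|---|---|
| Opening definition (any infection of an operated valve) | Yes | Infection seen on the valve |
| Criterion 1 (autopsy findings) | No | Subject is alive |
| Criterion 2 (Duke criteria) | Not available | A reoperation took place |

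The definition is met and the diagnostic rule is not. The row gives two answers for the same subject. The same happens with a reoperated subject who dies without an autopsy, which can occur because Section 9.10 asks for an autopsy report only where applicable.

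**Step 2: compare with other rows of Table 2.** Non-cerebral embolism can be documented at operation, at autopsy or clinically. Structural deterioration can be determined by reoperation, autopsy or clinical investigation. Valve thrombosis covers thrombus found at autopsy and thrombus found at operation. Operative evidence is accepted in all three. Only the endocarditis row omits it while also making reoperation a bar to the alternative criterion. This points to an omission, not a deliberate exclusion.

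**Step 3: follow a related leak.** An infective paravalvular leak in this subject is outside the major leak row ("exclusive of that associated with thrombosis or infection") and outside the non-structural row. The endocarditis row would take it in, but only if the case is accepted as endocarditis. If it is not, the leak belongs to no endpoint row.

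**Step 4: what still counts.** The reoperation is counted and, if the valve is removed, so is the explant. The indication is reported. Section 9.11 requires both the Device Explant and the Adverse Event forms when a complication leads to explant.

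**Step 5: weight of one case.** The documents give no expected endocarditis rate, margin or power for this endpoint, so there is no planned figure to reproduce. The inputs are N = 300 (planned maximum, Section 12) and the early and late formulas of Section 12.3. N = 240 is an assumed lower value for comparison. Full follow-up from day 30 to day 180 is also an assumption.

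- Early rate, one case: 1/N. For 300, 1/300 = 0.33%. For 240, 1/240 = 0.42%.
- Late patient-years: N × (180 − 30)/365.25. For 300, 300 × 150/365.25 = 123.2. For 240, 240 × 150/365.25 = 98.6.
- Late linearized rate, one case: 1/123.2 = 0.81 per 100 patient-years. For 240, 1/98.6 = 1.01 per 100 patient-years.
- Precision: recording 0 instead of 1 early case in 300 changes the estimate from 0.33% (exact 95% CI 0.01 to 1.84) to 0% (exact 95% CI 0 to 1.22).

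**The case against.** The strongest objection is that the text may be incomplete. A page break falls between the lead-in sentence and the list, and the condition in the second criterion is just what one would expect to see if a reoperation criterion had stood beside it. This cannot be excluded, so the source PDF should be checked first. Against it, the text available runs on continuously and no other section supplies the missing criterion.

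Second, the opening definition could let the CEC count the case, since Section 11.2 has it review potential endpoints as well as endpoints. That is so, and it is why the row is better called contradictory than a clear exclusion. But the sentence that follows ties the diagnosis to the listed criteria, and the CEC's role is left to a charter that is not part of the documents.

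Third, a subject who met the Duke criteria before surgery might be counted at that date, because the row does not say when the absence of reoperation is judged. This stands, and it limits the gap to infection first proven at reoperation.

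Fourth, the effect on related events is uneven. It is clear for leak. The embolism row excludes events in the presence of infection, with endocarditis given in brackets, so if a case is held not to be endocarditis that exclusion is not plainly triggered. The major bleeding and valve thrombosis rows have no infection exclusion of their own.

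A reader might infer that these cases disappear from the safety results, or are reported without their cause. The documents do not support that: reoperation and explant count them, the indication is recorded, serious events are reportable under Section 11.1, and Section 12.3 gives rates for other complications.

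**Conclusion.** The inconsistency stands on the text as available. Read literally, the endocarditis rate omits valve infection first proven at reoperation in a survivor, and an associated infective leak may be counted in neither place. The loss is to the endocarditis rate and its cause-specific label.

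The size is unknown. One missed case is worth 0.33 percentage points early, or about 0.8 per 100 late patient-years, with 300 subjects and full follow-up from day 30 to day 180. A reader might want to state a proportional understatement. That would need the number of endocarditis cases and the share who are reoperated survivors, and the documents give neither.

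The endpoint is descriptive and the primary cross-clamp comparison is unaffected. Because few events could be expected to settle the estimate at this sample size, a single classification decision can still move the reported figure from zero to non-zero, and the rule should be settled before adjudication.

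**What to change.** First check the source PDF for a criterion lost at the page break. If one covering reoperation findings is there, the point falls away.

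If there is none, make one of two changes to the endocarditis row of Table 2:

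1. Add findings of valve infection at reoperation or explant as a third criterion.
2. Delete the condition that opens the second criterion, so that the Duke criteria apply to every subject.

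Align the CEC charter with the chosen wording before any case is adjudicated.

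The cost is one line in Table 2 and the matching charter text. No new data are needed: Sections 10.2 and 11.1 already require source documents for safety endpoints, and Section 9.11 already requires the explant and adverse event forms. The reported endocarditis rate may be slightly higher.
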